2.3.4. Overall Benefit Risk Conclusion

In summary, the potential benefits of the MERINO:2 study include a deeper understanding of MTX's long-term effects and improved patient care. Given the nature of this observational study, we are providing a structured follow-up regardless of which treatment the participants ends up receiving. Decisions on treatment are discussed between participants and the treating physician.

More detailed information about the known and expected benefits and risks and reasonably expected adverse events (AEs) of MTX may be found in the summary of product characteristics (SmPC).

3. **Objectives and Endpoints**

In the MERINO:2 study, our main objectives are to explore the long-term effects of MTX in hand OA on structural progression, pain, and function. We will obtain hand radiographs and acquire patient-reported outcome measures through questionnaires (Table 1).

Table 1. Objectives and endpoints

| Objectives | Endpoints | | | | | |
|--|---|--|--|--|--|--|
| Primary | | | | | | |
| Effect of MTX on radiographic progression of erosive hand OA. | Progression in Verbruggen-Veys anatomical atlas score at 18 months | | | | | |
| Secondary | | | | | | |
| Effect of MTX on pain, function and life quality | Finger joint pain previous 48 hours (VAS) at 18 months Thumb base joint pain previous 48 hours (VAS) at 18 months Pain most painful finger joint previous 48 hours (VAS) at 18 months AUSCAN pain and function subscales at 18 months OMERACT-OARSI responder criteria at 18 months Patient-reported disease activity previous 48 hours (VAS) at 18 months EQ-5D at 18 months | | | | | |
| Effect of MTX on radiographic progression of hand OA. | KL grades OARSI atlas (osteophytes, joint space narrowing, erosions) | | | | | |

AUSCAN = Australian/Canadian hand index; EQ-5D = EuroQol 5 dimensions; KL = Kellgren and Lawrence; MHOQ = Michigan Hand Outcomes questionnaire pain and function subscales; OARSI = Osteoarthritis Research Society International; OMERACT-OARSI = Outcome Measures in Rheumatology Osteoarthritis Research Society International; VAS = visual analogue scale.

4. Study Design

4.1. Overall Design

The MERINO:2 is an investigator-initiated and open label observational study with one-year parallel group treatment with MTX in male and female adults with erosive hand osteoarthritis.

Eligible participants are those recruited to the MERINO-trial (EudraCT number 2019-004641-33, Clincaltrials.gov number NCT04579848, REK ID 2020/187524, CTIS number 2023-510523-30-00).

After the MERINO trial, participants may either continue treatment as usual or be prescribed MTX open-label (oral or s.c. 5-25mg per week as well as folic acid 1mg daily).

Especially of interest is to compare those who first receive placebo and then treatment as usual throughout the MERINO and MERINO:2 trials with those receiving MTX throughout the whole period, as this comparison will reflect the effect of long-term treatment with MTX over 2,5 consecutive years. Further, the Placebo→MTX crossover group will complement the data from the MERINO trial on shorter MTX treatment.

4.2. Scientific Rationale for Study Design

This study stands to fill a significant gap in OA research and could potentially guide future treatment protocols. OA is a slowly progressive disease but there are no studies examining the long-term (2 year) effect on structural progression of MTX treatment in erosive hand OA. The requests to explore MTX treatment after the MERINO trial prompted us to organize the follow-up within our outpatient clinic. This arrangement enables us to efficiently collect supplementary data. This approach also capitalizes on existing collaborations with our service departments, maximizing resource utilization and ensuring comprehensive patient care.

4.2.1. Patient Input into Design

The communication with users has over the years evolved into a strong partnership at Diakonhjemmet Hospital, where patient representatives, clinicians and researchers work together to improve the quality of care for people with rheumatic diseases. The collaboration continues in this project, where two patient representatives have been involved in the protocol development, and will also be consulted during the ongoing trial and before dissemination and publication of the results. Additionally, the project leader is also co-leader of the representative organization "REMEDY pasientråd".

4.3. Justification for Dose

Being an open-label observational study, the doses and treatment length of MTX will vary depending on the physicians and participants preferences. At the one-year control, we will use self-reported doses and The Norwegian Prescription Database (Reseptregisteret) to calculate the doses during the follow-up year.

4.4. End-of-Study Definition

The end of the study is defined as the date of the last scheduled procedure shown in the schedule of activities for the last participant in the study.

A participant is considered to have completed the study if the participant has completed one-time follow-up procedure shown in the SoA 30 months after entering the original MERINO trial.

5. Study Population

All participants entering the MERINO trial (see section 4.1) will be asked if they can voluntarily can provide a 30-month conventional radiographs and an electronic questionnaire. This results in four potential arms of the MERINO:2 trial, depending on the two former arms of the MERINO trial (Table 2).

The participants must be capable of giving signed informed consent as described in Appendix 1 which includes compliance with the requirements and restrictions listed in the informed consent form (ICF) and in this protocol.

We otherwise refer to the MERINO-protocol for study population description.

Table 2. Study Arms

| MERINO | MERINO:2 |
|--------------------|----------------------------------|
| 12 months | 18 months |
| MTX 10-20mg weekly | \rightarrow Treatment as usual |
| MTX 10-20mg weekly | → MTX 7,5-20mg weekly |
| Placebo | \rightarrow Treatment as usual |
| Placebo | → MTX 7,5-20mg weekly |

6. Study Intervention(s) and Concomitant Therapy

Study interventions are all pre-specified, investigational, and non-investigational medicinal products intended to be administered to the study participants during the study conduct.

6.1. Study Intervention Administered

Study intervention is defined as any investigational intervention(s), marketed product(s), or placebo intended to be administered to a study participant according to the study protocol (Table 3).

| ARM Name | Intervention | Co-medication |
|-------------------------|--|--|
| Intervention Name | МТХ | Folic acid |
| Producer | Pfizer | Orifarm Generics (Orifarm Healthcare AS) |
| ATC | L04A X03 | B03B B01 |
| Туре | Drug | Drug |
| Dose Formulation | Tablet | Tablet |
| Box size | 206 (x2) | 100 |
| Unit Dose Strength(s) | Methotrexate 2.5mg | 1mg |
| Frequency | Weekly | Daily |
| Dosage Level(s) | Decided by the treating physician, usually 10- 20mg weekly, with a down-scaled dose the first 2-3 weeks. | 1mg x 1 |
| Route of Administration | Oral | Oral |
| Use | Intervention | Minimize expected adverse reactions to methotrexate |
| IMP and NIMP | IMP | NIMP |
| Sourcing | Provided by local pharmacy | Provided by local pharmacy |
| Packaging and Labeling | Provided by local pharmacy according to national routines. | Provided by local pharmacy according to national routines. |

Table 3. Study interventions

6.1.1. Investigational medicinal product (IMP)

MTX 2.5 mg oral tablet; standard treatment is 15 mg x 1 per week the first two weeks, and then 20 mg x 1 per week to end of study. Physician may deviate from standard treatment dose, example in the case of adverse events, preferences by the participants or similar. Subcutaneous MTX can be provided and will be treated equally to oral tablets.

6.2. Preparation, Handling, Storage, and Accountability

Only participants enrolled in the study may receive study intervention, and only authorized pharmacy staff may supply, prepare, or administer study intervention.

6.3. Assignment to Study Intervention

The treating physician will decide, based on best clinical practice, if the patient should try MTX after the MERINO-trial. Central to this approach is the collaborative effort between the physician and participant, fostering an environment where patient perspectives are integral to treatment decisions. It will be emphasized by the physician prescribing MTX open-label that this is not evidence-based treatment until results of the MERINO-trial are published. We do, however, justify the continuation of MTX based on recent results from the METHODS trial (5). In the cases where the physician finds an indication for trying MTX after the MERINO trial, usual practice would be to try MTX for three months and then evaluate whether the patient should continue the treatment or not, based on synovitis scores and self-reported effects.

As described in section 5, this result in four groups in the MERINO:2 study, but since MTX treatment length and MTX doses could vary substantial in the observational time of the MERINO:2 study, we will adjust for this in the analyses.

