7.3. Lost to Follow-up

Not applicable. Examination at 18 months is voluntary. Missing data due to lost to follow-up will not be subject for data imputation.

8. Study Assessments and Procedures

- Study procedures and their timing are summarized in the SoA. Protocol waivers or exemptions are not allowed.
- To minimize questionnaires and procedures for the participants and the study team, we will use 12-month data from the MERINO trial as baseline data in the MERINO:2 study, including person characteristics, patient-reported outcome measures, clinical examination and imaging.
- Adherence to the study design requirements, including those specified in the SoA, is essential and required for study conduct.
- Procedures conducted as part of the participant's routine clinical management and obtained before signing of the ICF may be utilized for research purposes.
- In the event of a significant study-continuity issue (eg, caused by a pandemic), alternate strategies for participant visits, assessments, medication distribution and monitoring may be implemented by the sponsor or the investigator, as per local health authority/ethics requirements.

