9.1. Statistical Hypotheses

The primary objective is to demonstrate that MTX is superior to treatment as usual in achieving slower radiographic progression at 30 months. Thus, the null hypothesis to be tested in relation to the primary estimand is as follows:

• Null hypothesis: MTX treatment for 30 months is not different from placebo (12 months) and subsequent treatment as usual (18 months) with respect to the progression of Verbruggen-Veys scoring system in participants with erosive hand OA.

VS.

• Alternative hypothesis: MTX treatment for 30 months is different from placebo (12 months) and subsequent treatment as usual (18 months) with respect to the progression of Verbruggen-Veys scoring system in participants with erosive hand OA.

Secondary outcomes (1):

- Null hypothesis: MTX treatment for 30 months is not different from placebo (12 months) and subsequent treatment as usual (18 months) with respect to the progression of KL scale or OARSI atlas in participants with erosive hand OA.
- Alternative hypothesis: MTX treatment for 30 months is different from placebo (12 months) and subsequent treatment as usual (18 months) with respect to the progression of KL scale or OARSI atlas in participants with erosive hand OA.

Secondary objective (2)

- Null hypothesis: MTX is not different from placebo/treatment as usual with respect to change from baseline to 12/30 months in OMERACT-OARSI responder criteria, AUSCAN or EQ-5D-5L.
- Alternative hypothesis: MTX is different from placebo/treatment as usual with respect to change from baseline to 12/30 months in OMERACT-OARSI responder criteria, AUSCAN or EQ-5D-5L.

Multiplicity control is not relevant for the study.

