9.3. Statistical Analyses

Continuous variables will be subject to linear mixed models. Binary response variables will be analyzed using logistic regression models (possibly adjusting for within-subject dependencies by mixed model approaches). Analyses at the joint level will apply generalized estimating equations (GEE) to account for dependency between joints within one person. The SAP will detail these procedures.

The hypotheses will be evaluated by the p-value associated with the between group difference at study end. A conclusion of superiority will be made if the null hypothesis is rejected on an overall significance level of 5%. The SAP will detail these procedures, as well as alternative and further supportive evaluations, such as analyses including unbalanced baseline predictors or modifications of the linear regression model in case validity assumptions are not met.

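### Section 6.3 commits the analyses, without limit, to adjusting for MERINO:2 MTX length and dose; in the primary group contrast such covariates either damage the test or leave it unchanged

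*Protocol*

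**What the plan says.** Section 6.3 describes how MTX is given after MERINO. "The treating physician will decide, based on best clinical practice, if the patient should try MTX after the MERINO-trial", together with the participant. Where MTX is tried, usual practice is a three-month trial, after which the physician will "evaluate whether the patient should continue the treatment or not, based on synovitis scores and self-reported effects". The section then notes that four groups result and that, because "treatment length and MTX doses could vary substantial in the observational time of the MERINO:2 study, we will adjust for this in the analyses". No method is named, and the promise is not limited to supportive or secondary work.

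Section 9.1 sets the primary hypothesis: 30 months of MTX against 12 months of placebo followed by 18 months of treatment as usual, on Verbruggen-Veys progression. Section 9.3 states the decision rule: "The hypotheses will be evaluated by the p-value associated with the between group difference at study end", at an overall 5% level. Length and dose do not appear there. The one covariate example comes among the supportive evaluations left to the SAP, "such as analyses including unbalanced baseline predictors or modifications of the linear regression model".

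Section 8 says "we will use 12-month data from the MERINO trial as baseline data in the MERINO:2 study". Section 6.5 collects length and dose at 18 months, by questionnaire and from the prescription database.

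**The concern.** Treatment after MERINO is chosen, not randomised, so the primary contrast does need adjustment, but for the reasons behind the choice. Length and dose in MERINO:2 are not such reasons. They describe the last 18 of the 30 months of treatment that 9.1 sets out to test. They arise after the MERINO:2 baseline, and 6.3 itself says that continuation depends on synovitis and self-reported effect.

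The plainest way to carry out the promise is to add both as covariates beside the group term. Every treatment-as-usual participant then has 0 months and 0 mg, and every MTX participant has positive values. The group coefficient becomes the difference predicted at zero MERINO:2 exposure, where no MTX-then-MTX participant lies. The p-value that 9.3 relies on would then have little power for a real effect. If continuation goes with progression, the estimate could also move in either direction, depending on where the model is read.

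**Working it through.** The protocol has no figure to reproduce: section 9.5 says the sample size has no statistical basis, and no effect size, SD or group sizes are given. Everything below is illustrative.

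**Assumed inputs.** MTX-then-MTX group n1 against placebo-then-treatment-as-usual group n0: 30/40, 17/50 or 50/50. Length is uniform over 3 to 18 months, or 40% stop at 3 months and 60% reach 18. Dose is uniform over each range the protocol prints: "MTX 7,5-20mg weekly" (Table 2), 10-20 mg (Table 3) and 5-25 mg (section 4.1). Those ranges differ and need reconciling; all three are run without preferring one. Length and dose are taken as uncorrelated.

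**Standard error, uncentred covariates.**
SE ratio = sqrt[(1/n1 + 1/n0 + q/n1) / (1/n1 + 1/n0)], where q = mean²/variance of length + mean²/variance of dose, both in the MTX group.

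- Length 3-18: 10.5²/18.75 = 5.88. Dose 7.5-20: 13.75²/13.02 = 14.52. q = 20.40.
- n 30/40: 1/30 + 1/40 = 0.0583 and q/30 = 0.680. Ratio = sqrt(0.7383/0.0583) = 3.56.
- Length alone, 30/40: q/30 = 0.196. Ratio = sqrt(0.2543/0.0583) = 2.09.

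| n1/n0, length 3-18 | dose 7.5-20 | dose 10-20 | dose 5-25 | length alone |
|---|---|---|---|---|
| 30/40 | 3.56 | 4.45 | 2.87 | 2.09 |
| 17/50 | 4.03 | 5.05 | 3.23 | 2.32 |
| 50/50 | 3.35 | 4.18 | 2.70 | 1.98 |

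With the 40%/60% stopping pattern, mean length is 12, variance is 0.24 × 15² = 54, and mean²/variance is 2.67. At 50/50 and dose 5-25 (6.75), q = 9.42 and the ratio is 2.39, the lowest found. The range is therefore 2.4 to 5.1.

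**What the coefficient estimates.** Suppose benefit is proportional to months on MTX, with 1.0 SD for the full 30. At zero MERINO:2 exposure the model predicts 12/30 = 0.40 SD, at the mean length (12 + 10.5)/30 = 0.75 SD, and at 18 months 1.0 SD. A least-squares simulation used 30/40, dose 7.5-20, and a measured confounder 0.5 SD higher in the MTX group with a 0.3 SD effect on outcome. It gave:

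| Model | Estimate (SD) | SE | Power |
|---|---|---|---|
| Confounder only | -0.75 | 0.24 | 87% |
| Plus length and dose, group coefficient | -0.41 | 0.89 | 8% |
| Same model read at 18 months, length unrelated to outcome | -1.00 | 0.40 | 69% |

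**Bias when length tracks progression, no MTX effect.** With correlation r between slower progression and longer treatment, the slope on length is about -r/4.33 per month (SD of length = sqrt 18.75 = 4.33). The group coefficient shifts by about +r × 10.5/4.33 = +2.42r, and the 18-month reading by about -r × 7.5/4.33 = -1.73r. The simulation agrees, running slightly lower:

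| r | Group coefficient (false positives) | Read at 18 months (false positives) |
|---|---|---|
| 0.1 | +0.22 SD (5%) | -0.16 SD (6%) |
| 0.2 | +0.47 SD (8%) | -0.32 SD (13%) |
| 0.3 | +0.68 SD (12%) | -0.48 SD (23%) |

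Confounder adjustment without length and dose gave 0.00 SD and 5%.

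**Centred within the MTX group.** The centred covariates sum to zero in the MTX group and are zero in the other, so the group coefficient is the plain mean difference; only the residual variance can change. In a separate simulation at 40/40 with a constant 0.6 SD effect, power was 73.5% unadjusted, 75.1% centred and 12.4% uncentred.

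**The case against.** The strongest reply is that the harm belongs to a model the protocol never writes down. Section 6.3 says only that adjustment will be made, section 9 calls itself a summary, and choosing a method is normal SAP work. That stands in part: a missing method alone would be no finding, and nothing shows that the sponsor will fit the uncentred model. What remains is that 6.3 has already fixed what is adjusted for, in all analyses, and that this is part of the treatment under test.

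A reader might infer that 9.3 contradicts 6.3 by allowing only baseline covariates. The text does not support that: 9.3 gives an open-ended example and is silent on length and dose.

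A reader might also infer that any adjustment for length and dose wrecks the primary test. It does not. Centring removes the inflation. If the group term were the randomised arm, as the planned-intervention wording in 9.2 could suggest, exposure would be non-zero in both arms and inflation about 1.0 for similar arms. A four-group model with common slopes at 30/40/30/40 (dose 7.5-20, length 3-18) shares the slope information across 60 MTX users: sqrt[(0.0583 + 20.40/60)/0.0583] = 2.61, not 3.56.

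Finally, the bias figures use assumed correlations. Continuation is judged on synovitis and self-report, not radiographs, and at r = 0.1 false positives are close to nominal. The direction follows from the algebra; whether the bias arises at all is plausible but not shown by the protocol. Interest in differing exposure is legitimate, and the secondary analysis below serves it.

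**Conclusion.** The point holds as a defect of scope. Section 6.3 makes an unlimited commitment to adjust for post-baseline, partly response-driven components of the exposure, and 9.3 does not say whether this reaches the primary test. As covariate adjustment of the two-group contrast it is either harmful (uncentred: SE about 2.4 to 5.1 times larger; power 87% falling to 8% in the worked case; bias in either direction if length tracks progression) or without effect on the primary test (centred). Neither gives a reason to have it there.

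The sizes rest on assumed group sizes, exposure spreads, effect shape and correlations. The documents do not support saying that the primary analysis will be invalid, only that the wording permits an analysis that would be. It should be corrected before the SAP is final; confidence is medium because the SAP is not shown.

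**What to change.** State in 6.3 and 9.3 that MERINO:2 MTX dose and duration are not covariates in the primary group contrast. Use them only in a labelled secondary exposure-response analysis, with the caveat that duration is partly response-driven.

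Because MTX after MERINO is not randomised, adjust the primary contrast for confounders measured before that decision, from month-0 and month-12 data already collected. Month-12 values should not enter as plain covariates, since they follow the randomised year and may absorb part of its effect. Weighting for the post-MERINO decision within each MERINO arm is one option. It has not been tested here in groups this small, so the choice of method can be left to the SAP.

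The cost is one sentence in each section and one secondary model, with no new data; the confounder method takes further SAP work. The downside is that the contrast averages over varying treatment length and is diluted by early stoppers (-0.75 SD rather than -1.0 SD in the worked case), and residual confounding remains. Whether to redefine the groups or reword 9.1 is a separate estimand choice for the sponsor.

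Editorial: section 4.3 speaks of a one-year control and a follow-up year when describing the dose calculation. Reconcile this with the 18-month period from month 12 to month 30 in 6.5, Table 2 and the schedule of activities.

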6.4. Blinding

This is an open-label study; potential bias will be reduced by blinding the researcher who will interpret and score the radiographs.

6.5. Study Intervention Compliance

Treatment length and doses will be assessed by questionnaires at 18 months as well as data from the The Norwegian Prescription Database (Reseptregisteret).

6.6. Dose Modification

The treating physician may decide on other doses of MTX than 20mg per week according to standard clinical practice.

6.7. Continued Access to Study Intervention after the End of the Study

There are currently no planned extension studies, but the participants have the possibility for continued access to the study intervention beyond completion of the study at the patient level.

6.8. Treatment of Overdose

There have been documented cases of death attributable to MTX. These have often involved patients taking MTX as a daily, rather than weekly dose due to patient, clinician and/or pharmacy error. In the United Kingdom, the National Patient Safety Authority released a report in 2004 on MTX prescribing after 25 deaths and 26 incidents of serious harm in the preceding

decade. In some of these cases, even once the error was identified, patients died due to ongoing deterioration after MTX withdrawal.

For this study, any dose of MTX greater than 30mg/week will be considered an overdose, but there is no clear dose cut-of as for when overdose symptoms can occur, especially since this is regarded a low dose treatment of MTX. No specific treatment for an overdose is recommended.

In the event of an overdose, the investigator or treating physician should:

- 1. Contact the Medical Monitor immediately.
- 2. Closely monitor the participant for any AE/SAE and laboratory abnormalities.
- 3. Document the quantity of the excess dose as well as the duration of the overdose in the electronic patient journal.

Decisions regarding dose interruptions or modifications will be made by the investigator in consultation with the Medical Monitor based on the clinical evaluation of the participant.

6.9. **Prior and Concomitant Therapy**

- Prior therapy is recorded in the MERINO trial eCRF.
- All concomitant medication at 18 months in the MERINO:2 study should be recorded in the eCRF.
- Intra-articular corticosteroids during the MERINO:2 study will be registrered from the outpatient clinic notes.

7. Discontinuation of Study Intervention and Participant Discontinuation/Withdrawal

Discontinuation of the study as a whole is detailed in Appendix 1.

